4.2 METHOD OF TREATMENT ASSIGNMENT AND BLINDING

This is an open-label study, therefore no blinding will be used.

Patients will be assigned to a dose level in the order in which they are enrolled into the study. Treatment assignment across clinical sites will be managed manually.

4.3 STUDY TREATMENT AND OTHER TREATMENTS RELEVANT TO THE STUDY DESIGN

The investigational medicinal product (IMP) for this study is RO7234292.

Patients will receive two IT doses of the same dose strength of RO7234292 at an interval of 28 days during the treatment period (Day 1 and Day 29). Each dose of RO7234292 will be administered as a single IT bolus injection.

4.3.1 Study Treatment Formulation, Packaging, and Handling

4.3.1.1 RO7234292

RO7234292 drug product is provided as 6.0 mg/mL RO7234292 for IT injection. The drug product is supplied as sterile, preservative-free liquid in a 20-mL single-use vial containing 10 mL of 6.0 mg/mL RO7234292 drug product having a pH of approximately 7.2. In addition to the active drug substance, the liquid is also composed of sodium dihydrogen phosphate dihydrate, sodium phosphate dibasic anhydrous, sodium chloride, potassium chloride, calcium chloride dihydrate, and magnesium chloride hexahydrate.

RO7234292 should be prepared by a pharmacist using aseptic technique. RO7234292 vials do not contain antimicrobial preservatives. Therefore, care must be taken to ensure that the solution for infusion is not microbiologically compromised during preparation. All transfer procedures require strict adherence to aseptic techniques. Do not use RO7234292 beyond the use by date stamped on the carton.

The study drug must be stored according to the details on the product label. The recommended storage conditions for RO7234292 drug product is between 2°C to 8°C (36°F to 46°F), protected from light.

RO7234292 will be provided by Roche to investigational centers on a regular basis. Investigational product packaging will be overseen by the Roche Global Clinical Trial Supplies department. The supply will be packed bearing labels with the identification required by local regulations and in accordance with Roche standards and local regulations.

Upon arrival of investigational products at the site, site personnel should check the investigational product for damage and verify proper identity, quantity, integrity of seals, and temperate conditions, and report any deviations or product complaints to the monitor upon discovery.

For information on the formulation, study drug preparation, and handling of RO7234292, see the pharmacy manual.

4.3.1.2 Diluent

RO7234292 diluent for IT injection is provided as a sterile, preservative-free liquid in a 20-mL single-use vial containing 10 mL of RO7234292 diluent having a pH of approximately 7.2. The liquid is also composed of sodium dihydrogen phosphate dihydrate, sodium phosphate dibasic anhydrous, sodium chloride, potassium chloride, calcium chloride dihydrate, and magnesium chloride hexahydrate.

RO7234292 diluent must be stored according to the details on the product label. The recommended storage conditions for RO7234292 drug product is between 2°C to 8°C (36°F to 46°F), protected from light.

RO7234292 diluent will be provided by Roche to investigational centers on a regular basis. Investigational product packaging will be overseen by the Roche Global Clinical Trial Supplies department. The supply will be packed bearing labels with the identification required by local regulations and in accordance with Roche standards and local regulations.

Upon arrival of RO7234292 diluent at the site, site personnel should check the investigational product for damage and verify proper identity, quantity, integrity of seals, and temperate conditions, and report any deviations or product complaints to the monitor upon discovery.

For information on the formulation, study drug preparation, and handling of RO7234292 diluent, see the pharmacy manual.

4.3.2 Study Treatment Dosage, Administration, and Compliance

The treatment regimens are summarized in Section [3.1](#).

Each dose of RO7234292 will be administered as a single IT bolus injection of 20 mL.

Administration of the first dose will occur via an IT catheter inserted at baseline and also used for CSF sampling. Administration of the second dose will occur via a lumbar puncture using a needle inserted into the L3/L4 space, although placement at a different level (either in the space above or the space below) is allowed if patient anatomy or clinical judgment dictates.

For details on the lumbar puncture and IT bolus dosing procedure, please refer to the lumbar puncture manual and instructional video. Of note, Investigators will perform a predose neurological examination, including fundoscopy, to rule out increased intracranial pressure prior to performing the lumbar puncture, which is a contraindication to the procedure.

Patients will be discouraged from resting supine after the lumbar puncture procedure and will be encouraged to mobilize immediately by walking around at a minimum and, if feasible, walking briskly.

Patients may receive doses, which have previously been investigated in the Phase I/IIa MAD study (ISIS 443139-CS1) or OLE study (ISIS 443139-CS2), ranging from 30 to

120 mg of RO7234292. The decision to determine which doses will be explored after the initial three dose levels of 120 mg, 60 mg, and 30 mg will be made following review of all relevant safety, tolerability, PK, and biomarker data collected from all previous patients.

The patient's bladder must be completely emptied at the time of study drug administration.

No dosage adjustment from planned treatment is permitted in this study. If a patient misses a dose visit, the Investigator should contact the Medical Monitor to determine appropriate continuation of the patient in the study.

Cases of accidental overdose or medication error, along with any associated adverse events, should be reported as described in Section [5.4.4](#).

Guidelines for treatment interruption or discontinuation for patients who experience adverse events are provided in Section [5.1.3](#).

4.3.3 Investigational Medicinal Product Accountability

All IMPs required for completion of this study (RO7234292) will be provided by the Sponsor where required by local health authority regulations. The study site will acknowledge receipt of IMPs supplied by the Sponsor to confirm the shipment condition and content. Any damaged shipments will be replaced.

IMPs will either be disposed of at the study site according to the study site's institutional standard operating procedure or be returned to the Sponsor with the appropriate documentation. The site's method of destroying Sponsor-supplied IMPs must be agreed to by the Sponsor. The site must obtain written authorization from the Sponsor before any Sponsor-supplied IMP is destroyed, and IMP destruction must be documented on the appropriate form.

Accurate records of all IMPs received at, dispensed from, returned to, and disposed of by the study site should be recorded on the Drug Inventory Log.

4.3.4 Continued Access to RO7234292

It is intended that patients will be eligible to receive RO7234292 as part of an OLE study (Study BN40955) as described in Section [3.1](#).

The Sponsor will offer continued access to Roche IMP (RO7234292) free of charge to eligible patients in accordance with the Roche Global Policy on Continued Access to IMP, as outlined below.

A patient will be eligible to receive Roche IMP (RO7234292) after completing the study if all of the following conditions are met:

- The patient has a life-threatening or severe medical condition and requires continued Roche IMP treatment for his or her well-being.
- There are no appropriate alternative treatments available to the patient.
- The patient and his or her doctor comply with and satisfy any legal or regulatory requirements that apply to them.

A patient will not be eligible to receive Roche IMP (RO7234292) after completing the study if any of the following conditions are met:

- The Roche IMP is commercially marketed in the patient's country and is reasonably accessible to the patient (e.g., is covered by the patient's insurance or wouldn't otherwise create a financial hardship for the patient).
- The Sponsor has discontinued development of the IMP or data suggest that the IMP is not effective for HD.
- The Sponsor has reasonable safety concerns regarding the IMP as treatment for HD.
- Provision of the Roche IMP is not permitted under the laws and regulations of the patient's country.

The Roche Global Policy on Continued Access to IMP is available at the following website:

http://www.roche.com/policy_continued_access_to_investigational_medicines.pdf

4.4 CONCOMITANT THERAPY

Concomitant therapy consists of any medication (e.g., prescription drugs, over-the-counter drugs, vaccines, herbal or homeopathic remedies, and nutritional supplements) used by a patient in addition to protocol-mandated treatment from screening to the study completion/discontinuation visit. All such medications should be reported to the Investigator and recorded on the Concomitant Medications electronic Case Report Form (eCRF) at each clinical visit.

4.4.1 Permitted Therapy

Patients are permitted to use the following therapies during the study:

- Contraceptive agents.
- Supplements (e.g., coenzyme Q10, vitamins, creatine) if the dose has been stable for at least 6 weeks prior to screening, and the dose is not anticipated to change during the study.

- Antipsychotics only if prescribed for motor symptoms or mood stabilization (i.e., irritability or aggressive behavior) if the dose has been stable for at least 12 weeks prior to screening, and the dose is not anticipated to change between screening and the start of treatment initiation.

If clinically indicated, dose changes or medication starting and stopping can occur as per Investigator judgment during the course of the study.
- Antidepressants or benzodiazepines if the dose has been stable for at least 12 weeks prior to screening, and the dose is not anticipated to change between screening and the start of study treatment.

If clinically indicated, dose changes or medication starting or stopping can occur as per Investigator judgment during the course of the study.
- Anti-epileptics if given for mood stabilization and/or pain.
- Aspirin at doses ≤ 81 mg/day.
- Local anesthesia for the lumbar puncture procedure, depending on institutional guidelines.

Sedation may not be used for lumbar puncture.

4.4.2 Prohibited Therapy

Use of the following concomitant therapies is prohibited:

- Current use of tetrabenazine, valbenazine, or deutetrabenazine.
- Experimental agents or marketed HD agents at experimental doses that are being tested for the treatment of HD, including but not limited to, cholinesterase inhibitors, memantine, amantadine, and/or riluzole.
- Antiplatelet or anticoagulation therapy, including, but not limited to, aspirin, (unless ≤ 81 mg/day), clopidogrel, dipyridamole, warfarin, dabigatran, rivaroxaban, and apixaban.
- Sedation for lumbar puncture or IT bolus procedures in the study.
- *Use of anti-anxiety medication is prohibited during scheduled MRI scans. Anti-anxiety medication used to prevent movement disorder to allow successful MRI scan is not permitted in this study, as movement disorder too severe to scan under drug-free conditions is an overall study exclusion criterion.*

4.5 STUDY ASSESSMENTS

The schedules of activities to be performed during the study are provided in [Appendix 1](#) and [Appendix 2](#). All activities should be performed and documented for each patient.

Patients will be closely monitored for safety and tolerability throughout the study. Patients should be assessed for toxicity prior to each dose; dosing will occur only if the clinical assessment and local laboratory test values are acceptable.

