1.3 STUDY RATIONALE AND BENEFIT-RISK ASSESSMENT

Presently, there are no therapies available to stop or slow the clinical progression of HD, which is relentless until patients experience premature death. The ASO RO7234292 is designed to target the cause of HD and offers the potential to meet this unmet medical need.

To date, non-clinical and clinical data have been generated to support further investigation of RO7234292 in patients with early manifest HD.

Building on the completed Phase I/IIa study and the ongoing OLE Study BN40697, this Phase I study (BP40410) will collect clinical PK and pharmacodynamics (PD) data to characterize the magnitude and duration of CSF mHTT reduction after short-term IT bolus dosing with RO7234292. This study will also further inform the semi-mechanistic population PK/PD model that has been developed on the basis of the currently available clinical and non-clinical data. Ultimately, this will guide clinical decision-making about optimal treatment regimens by providing information about the relationship between RO7234292 dosing and the time course of mHTT reduction, which could not be obtained any other way.

This study is open-label and will be conducted in an early manifest HD population over 8 months including an approximately 4-week screening period and an approximately 28-week study period.

Patients will be admitted to the site in the afternoon/evening of Day -2 or in the morning of Day -1 to begin the first in-house period of the study. After completing the safety assessments *including Holter ECG*, an IT catheter will be inserted *on the morning of Day 1* to facilitate frequent CSF sampling and IT bolus dosing of RO7234292. After

baseline CSF sampling, a single dose of RO7234292 will be given, after which sampling will continue for a further 48 hours before the catheter is removed. The patients will be discharged on Day 4 after all assessments have been completed.

Patients will return to the site for the second in-house period in the afternoon/evening of Day 28 or in the morning on Day 29 and will be discharged on Day 29 after all assessments have been completed. The second dose of RO7234292 will occur via a lumbar puncture on Day 29.

Patients will return to the site for daily visits on Days 30, 43, 71, 127, and the follow-up visit (6 months after the last study drug administration).

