4.5.6 Laboratory, Biomarker, and Other Biological Samples

Samples for the following laboratory tests will be sent to the study site's local laboratory for analysis:

- Coagulation: INR, aPTT, and PT.
- Platelet count.
- Pregnancy test.

All women of childbearing potential will have a serum pregnancy test at screening (central laboratory). Urine pregnancy tests (local laboratory) will be performed at specified subsequent visits. If a urine pregnancy test is positive, it must be confirmed by a serum pregnancy test (analyzed at a central laboratory).

- CSF safety sample: cell count (red blood cell [RBC] and white blood cell [WBC]), glucose, protein, and culture.
- *Blood for C-reactive protein (CRP), erythrocyte sedimentation rate (ESR)*
- *Hematology: WBC count, RBC count, platelet count, hemoglobin, hematocrit, and differential count (neutrophils, eosinophils, basophils, monocytes, lymphocytes).*
- *Skin and nasal swab for MRSA screening.*

Samples for the following laboratory tests will be sent to a central laboratory for analysis:

- Serum chemistry panel: bicarbonate, sodium, potassium, chloride, glucose, blood urea nitrogen, creatinine, total protein, albumin, phosphorus, calcium, total and direct bilirubin, alkaline phosphatase, alanine aminotransferase (ALT), aspartate aminotransferase (AST), uric acid, gamma-glutamyl transferase, and creatine phosphokinase.
- Hormone panel (female subjects only): follicle-stimulating hormone and Estradiol.
- Thyroid panel: thyroid-stimulating hormone and free thyroxine (also known as T4) levels.
- Viral serology: hepatitis B virus surface antigen, hepatitis C virus antibody, HIV-1 antibody, HIV-2 antibody.
- Serum pregnancy test.

Serum pregnancy tests will be performed on women of childbearing potential at screening and subsequent visits to confirm a positive urine pregnancy test (if applicable).

- Urinalysis including dipstick (pH, specific gravity, glucose, protein, ketones, blood) and microscopic examination (sediment, RBCs, WBCs, casts, crystals, epithelial cells, and bacteria).
- CSF, urine, and plasma samples for PK analyses and metabolite identification.
- Blood samples for immunogenicity analysis.
- Blood sample for determination of CAG repeat length in HTT for patient eligibility.

- Blood sample for clinical genotyping for DNA extraction to enable exploratory analysis and assay development with respect to genes related to HTT function and severity of the disease.

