5.1.3.3 Management Guidelines

Guidelines for management of specific adverse events are outlined in [Table 1](#). Additional guidelines are provided in the subsections below.

Initial clinical laboratory tests with results meeting criteria for withholding study drug must be repeated on new specimens as soon as possible, and results must be available prior to administering the next dose of study drug. In general, patients who do not reach the stopping rule may continue dosing; however, the Investigator and Sponsor should confer as to whether additional close monitoring of the patient is indicated.

Table 1 Guidelines for Management of Patients Who Experience Adverse Events

Event	Action to Be Taken

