Thrombocytopenia	
 • If platelet count is $\leq 100,000/\text{mm}^3$: 
 Monitor platelet count weekly. • If platelet count is $\leq 75,000/\text{mm}^3$ and $> 50,000/\text{mm}^3$ in the absence of major bleeding or clinically relevant non-major bleeding: 
 Withhold study drug until the platelet count has recovered to $> 100,000/\text{mm}^3$. The suitability of the patient for continued dosing and frequency of monitoring should be discussed with the Medical Monitor. • If platelet count is $\leq 50,000/\text{mm}^3$: 
 Permanently discontinue. Monitor platelet counts daily until two successive values show improvement. Then monitor every 2 to 3 days until platelet count is stable, and at least weekly until platelet count returns to normal. Administration of steroids may be considered for patients whose platelet count is $< 25,000/\text{mm}^3$.
Decreased renal function	
 • Withhold study drug in the event of a persistent (> 2 weeks) decrease of eGFR or CrCl or increase in creatinine, as defined below: 
 1. eGFR or CrCl $< 60 \text{ mL/min}/1.73 \text{ m}^2$. 2. Creatinine level increase of $2.0 \times$ above baseline. • Study Drug may be resumed when follow-up test results show that the patient no longer meets the dose interruption criteria.

ALT=alanine aminotransferase; AST=aspartate aminotransferase; CrCl=creatinine clearance; CSF=cerebrospinal fluid; eGFR=estimated glomerular filtration rate; INR=international normalized ratio; ULN=upper limit of normal; WBC=white blood cell.

Table 1 Guidelines for Management of Patients Who Experience Adverse Events (cont.)

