Elevated liver enzymes	
 ALT or AST is $> 3 \times$ ULN: 
 Monitor weekly until ALT and AST return to $\leq 1.2 \times$ ULN. Further investigation into the liver enzyme elevations may include hepatitis serologies and other diagnostic tests at the discretion of the Investigator in consultation with the Medical Monitor. Withhold study drug in the event of liver enzymes that meet the following criteria without an alternative explanation (as discussed with the Medical Monitor): 
 ALT or AST $> 5 \times$ ULN. ALT or AST $> 3 \times$ ULN, combined with total bilirubin $> 2 \times$ ULN or INR > 1.5. ALT or AST $> 3 \times$ ULN coinciding with new appearance of fatigue, nausea, vomiting, right upper quadrant pain or tenderness, fever, rash, and or concomitant eosinophilia. Discontinue study drug permanently if levels do not return to baseline after 30 days.
------------------------	--

ALT=alanine aminotransferase; AST=aspartate aminotransferase; CrCl=creatinine clearance; CSF=cerebrospinal fluid; eGFR=estimated glomerular filtration rate; INR=international normalized ratio; ULN=upper limit of normal; WBC=white blood cell.

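### For kidney or liver abnormalities arising after Day 4, the documents do not ensure that Table 1's withholding rules can act on the Day 29 dose

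*Protocol*

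**What the plan says.** Protocol Section 4.3 gives two doses, on Day 1 and Day 29. Section 4.5 calls for a toxicity assessment before each one and adds that "dosing will occur only if the clinical assessment and local laboratory test values are acceptable".

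Section 4.5.6 divides the tests between two laboratories. Coagulation, platelets, hematology, CRP and ESR are local. Chemistry comes under the other list: "Samples for the following laboratory tests will be sent to a central laboratory for analysis". Its first entry is "Serum chemistry panel: bicarbonate, sodium, potassium, chloride, glucose, blood urea nitrogen, creatinine, total protein", and that entry goes on to include bilirubin, ALT and AST.

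Section 1.3 sets the timing of the second stay: "Patients will return to the site for the second in-house period in the afternoon/evening of Day 28 or in the morning on Day 29".

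Table 1 in Section 5.1.3.3 holds the two rules.
- Kidney: "Withhold study drug in the event of a persistent (> 2 weeks) decrease of eGFR or CrCl or increase in creatinine".
- Liver: "Withhold study drug in the event of liver enzymes that meet the following criteria without an alternative explanation". This rule has no duration condition. Table 1 also asks for weekly ALT and AST tests once either exceeds 3 x ULN.

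The text above Table 1 says that laboratory results meeting withholding criteria are to be repeated on fresh specimens, and that "results must be available prior to administering the next dose of study drug".

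**The concern.** Only one dose follows the first, so a withholding rule has one opportunity to change treatment. For that it needs a recent result that someone must look at before dosing.

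For coagulation and platelets the protocol provides this. Section 4.5.5 and footnote aa of Appendix 1 have them run locally within 72 hours before a lumbar puncture and reviewed. Chemistry has no equivalent. It is central, it is sampled very close to the dose, and it falls outside the laboratory values named in the Section 4.5 check.

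Sections 5.1.2.4 and 5.1.2.5 list kidney and liver effects as potential risks and refer to Appendix 1 for monitoring and Table 1 for management. If the two do not connect at Day 29, part of that safeguard exists on paper only.

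**Working it through.** No sample size or power figure is involved. The check reads the chemistry row of the schedules against the dosing days.

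**Inputs**
- Dosing days: 1 and 29 (Section 4.3).
- Chemistry in Appendix 1: screening, Day -1, Day 2, Day 4, Day 28, Day 43, Day 71, Day 127, follow-up, early termination. Appendix 2 agrees for the in-house days and shows none on Day 29.
- Windows: ±2 days on Day 28 and on Day 29, for exceptional circumstances (Appendix 1, footnote b).
- Ideal puncture times: 8:00 a.m. to 3:00 p.m. (Section 4.5.5).
- Kidney persistence condition: more than 14 days (Table 1).
- Central turnaround: not stated. It must be assumed; a plausible range is the same day to several days.

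**Time from each sample to the second dose**

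| Sample | Days to Day 29 |
|---|---|
| Day 2 | 29 − 2 = 27 |
| Day 4 | 29 − 4 = 25 |
| Day 28, nominal | 29 − 28 = 1 |
| Day 28 sample on Day 26, dose on Day 31 (both windows used in full) | 31 − 26 = 5 |

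In clock time, a sample at noon on Day 28 and a puncture at 3:00 p.m. on Day 29 are 24 + 3 = 27 hours apart. Evening admission shortens this. For patients admitted on the morning of Day 29, the documents do not say when the Day 28 sample is drawn. If it is drawn on arrival, only hours remain.

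**Liver rule**
- Abnormal on Day 2 or Day 4: 25 to 27 days remain for reporting, repeat and weekly tests. The rule can stop the second dose.
- First abnormal after Day 4: the first scheduled detection is Day 28. At the nominal gap the rule acts only if the central result is back within about a day. A same-day turnaround would suffice; one of several days would not.

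**Kidney rule**
- Day 2 to Day 4 is 4 − 2 = 2 days, too short to show persistence.
- Day 2 to Day 28 is 28 − 2 = 26 days and Day 4 to Day 28 is 28 − 4 = 24 days. Both exceed 14, but using them before dosing needs the Day 28 result in time, or an unscheduled repeat.
- First seen on Day 28: the earliest day on which more than 14 days have passed is 28 + 15 = Day 43. That is after the second dose, even one given on Day 31, whatever the turnaround.

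**The other checks**
The repeat-test requirement above Table 1 and the weekly liver tests both start from an abnormal result that is already known. Neither requires the first Day 28 result to be seen before dosing. If a Day 28 result is known to meet a criterion, a repeat is then needed before the dose, which is hard within a day.

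**The case against.** The strongest reply is that the rules do work for much of the interval. Day 2 and Day 4 results leave more than three weeks. The liver rule needs no persistence and brings weekly tests. The repeat requirement covers all laboratory tests, not only local ones, so Section 4.5 is not the sole check. Section 5.3.5.5 makes the investigator responsible for reviewing all laboratory findings, and Section 9.4 says local laboratories are used for routine monitoring. The laboratory manual, which is not among the documents, may set a fast turnaround. The protocol also reports no clinically significant kidney or liver changes in the completed Phase I/IIa study. In the extension study it reports one related case of proteinuria, which resolved, and no drug-related clinically significant liver abnormality.

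Much of this stands. A reader might infer that the rules cannot act on the second dose at all, or that a patient meeting a criterion on Day 28 will be dosed before the result arrives. The documents support neither: early abnormalities can be acted on, and the second inference depends on a turnaround that is not given. Nor is Day 28 the last chemistry of the study; it is only the last before the second dose. And a patient whose kidney change is first seen on Day 28 does not yet meet Table 1's criterion, so dosing that patient follows the table as written, wherever the sample is tested.

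The reply does not close the gap. The duty to review findings carries no deadline before dosing. The general sentence on local laboratories does not override the specific assignment of chemistry to the central one. The earlier safety record bears on how often the gap would matter, not on whether it exists.

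**Conclusion.** The point holds for abnormalities arising after Day 4. Nothing requires a chemistry result from that interval to be seen before the only remaining dose, and a site that follows the text could give that dose with its latest reviewed chemistry 25 days old. The schedule is the same for every patient (12 planned, at most 20), with one such decision each. The number of patients actually affected is probably small and cannot be estimated from the documents.

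Whether the Day 28 result would arrive in time rests on the unstated central turnaround, against a nominal gap of about a day or less and at most 5 days under exceptional use of both windows. The persistence point does not depend on turnaround: a kidney change first seen on Day 28 cannot meet the condition by Day 29. This is a modest but real mismatch between a stated safety rule and the schedule meant to serve it, and it is worth correcting.

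**What to change.** Reconcile Sections 4.5, 4.5.6 and 5.1.3.3 (including the kidney and liver rows of Table 1) with Appendices 1 and 2 on two matters.

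1. Time and process the chemistry sample before the second dose so that creatinine, bilirubin, ALT and AST are available for the toxicity assessment Section 4.5 already requires, and make the wording of that check agree. The 72-hour local arrangement used for coagulation and platelets is one logistical model; an earlier central draw with a stated turnaround is another.
2. State how a condition of more than two weeks is meant to operate when one scheduled chemistry sample falls between Day 4 and the second dose.

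Which results lead to withholding is for the clinical team; this point proposes no rule.

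The cost is protocol wording plus either an earlier draw or a local run of four analytes per patient at one visit. The small drawback is a local and a central value for the same visit; the plan would then need to say which one is analysed.
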